9.3. Treatment discontinuation

The investigator has the right to discontinue study treatment if he/she feels that it is in the best interests of the patient or due to safety concerns.

Study drug will be stopped immediately if there is disease recurrence confirmed by CT, histology or cytology, and in the event of an SAE unequivocally related to study drug (or at the discretion of the investigator if the relationship of SAE to the study drug cannot be established with certainty at the time of reporting).

The reasons for treatment discontinuation will be documented. Patients with their treatment discontinued will continue to be followed up until 5 years after randomisation.

Even if a patient chooses not to adhere to the treatment assignment or data collection schedule, every effort should be made to follow patient for the protocol objectives until the end of the study.

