2 STUDY OBJECTIVES

Primary objective

Null hypothesis: Among subjects with Dukes C or high risk Dukes B colorectal cancer, Disease Free Survival (DFS) between those randomised to Aspirin and those randomised to placebo control is equal.

Alternative hypothesis: Among subjects with Dukes C or high risk Dukes B colorectal cancer, DFS between those randomised to Aspirin and those randomised to placebo is not equal.

Primary objective: To compare DFS between the group randomised to Aspirin with the group randomised to placebo control in subjects with Dukes C or high risk Dukes B colorectal cancer.

Secondary objectives

1. To compare the DFS between the group randomised to Aspirin with the group randomised to placebo control in subjects with high risk Dukes B and Dukes C colon cancer.
2. To compare the overall survival (OS) between the group randomised to Aspirin with the group randomised to placebo control in subjects with Dukes C or high risk Dukes B colorectal cancer.

Exploratory objectives

1. To compare the DFS and OS between the group randomised to Aspirin with the group randomised to placebo control in subjects with Dukes C or high risk Dukes B colorectal within the following subgroups:
 - a. Baseline variables
 - i. Country.

Countries with small sample size (less than 25) will be pooled under 'Others' or with countries with similar ethnic population.

- ii. Resected high risk Dukes B colon cancer, Dukes C colon cancer, colon cancer and rectal cancer.
- iii. Exposed to Oxaliplatin, not exposed to Oxaliplatin.
- iv. Ethnicity (East Asian, South Asian, Caucasian and Others).
- v. Type of surgery (laparoscopic surgery, open surgery).
- vi. Chemotherapy duration (<3 months, 3-6 months, >6 months).
- vii. Age group (<70, ≥70).

b. Translational variables

- i. Compliant subjects, non-compliant subjects.

Compliant subject is defined as an individual who is on the study drug for at least 70% of days in first year from randomisation or up to treatment discontinuation or recurrence, whichever is earlier.

- ii. Duration of exposure to study drug (<1 year, 1-2 years, >2 years).

The duration of exposure to study drug during the treatment period is defined as the number of days from the first dose to the last dose excluding days of interruptions, i.e. "duration of exposure" = "last dosing date" – "first dosing date" – "days off medication" + "1 day".

- iii. PIK3CA mutations (mutant PIK3CA, wild-type PIK3CA)

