3.2 Treatment Schedule

A total of 1587 subjects will be randomised from multinational centres. After randomisation, subject will have 3-monthly assessments for 3 years (month 3 to month 36) followed by 6-monthly assessments for additional 2 years (month 42 to month 60). Subjects who consent to continue information collection after month 60 will have vital data captured via review of medical records or phone call.

The study drug, oral Aspirin 200 mg/ placebo 200 mg once a day, should begin immediately but no later than 2 weeks of randomisation. The study drug will be stopped immediately if there is a disease recurrence confirmed by CT, histology or cytology. In the event of SAE related to the study drug, the study drug will be stopped immediately.

The investigator has the right to discontinue study treatment if he/she feels that it is in the best interests of the subject or due to safety concerns. The reasons for treatment discontinuation will be documented. All subjects, including subjects who discontinued from study treatment, will continue to be followed for 5 years after randomisation, unless the subject is lost to follow up, died or withdrew consent.

3.3

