4.2 Analysis Populations

All efficacy analyses will be carried out on modified intention-to-treat (mITT) basis, i.e., all subjects who signed the informed consent form for the study enrolment and commenced study treatment after the randomisation are to be analysed as randomised.

As part of sensitivity analysis, efficacy analysis on per-protocol basis will also be performed. Per-protocol analysis consists of subjects included in the mITT population after excluding those with major protocol deviation and those who were compliant <70% of the days in the first year from randomisation. Compliance has been defined in section 2.

Subjects included in safety data analysis are those who received at least one dose of the study treatment drug. These subjects will be grouped and analysed as actually treated.

The number of subjects screened, randomised to the study treatment, completing each subsequent study period including up to 3-year treatment and 5-year follow-up will be summarised in a CONSORT flow chart.

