For all subgroup analyses of DFS and OS by different countries, tumour types (high risk Dukes B colon, Dukes C colon, colon, rectal), adjuvant chemotherapy types (exposed to Oxaplatin, not exposed to Oxaliplatin), ethnic groups (East Asian, South Asian, Caucasian, Others), type of surgery (laparoscopic surgery, open surgery), chemotherapy duration (<3 months, 3-6 months, >6 months), age group (<70, ≥ 70), levels of compliance (<70%, $\geq 70\%$), duration of exposure to drug (<1 year, 1-2 years, >2 years), PIK3CA mutations (mutant PIK3CA, wild-type PIK3CA) and COX-2 expression (positive for COX-2 overexpression, negative for COX-2 overexpression), tests for interactions between treatment group and the subgroup variable of interest will be conducted first. As the subgroups under tumour types are not mutually exclusive, the test for interaction will be based on the original mutually

exclusive groups. Results of subgroup analyses will be presented in forest plots. Subgroup analyses will be considered as exploratory.

Appropriateness of Cox PH regression model will be checked using graphical method of log-log survival curves for treatment indicator and each covariate. Continuous covariate will be dichotomised at mean value to check for the PH assumption. PH assumption will be considered not satisfied if there is strong evidence of non-parallelism in the log-log survival curves. Should there be at least one covariate not satisfying the PH assumption, “no-interaction” (i.e. estimated coefficients not varying by stratum) stratified Cox regression model will be used instead. The model will be stratified by strata formed after combining categories of all covariates which did not satisfy the PH assumption. Covariate(s) which satisfies the PH assumption will remain included in the stratified model. If the treatment indicator is found to not satisfy the PH assumption, time-varying HR will be obtained by partitioning the follow-up time into 1-year intervals.

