Note: Compliant subject is defined as an individual who is on study drug for at least 70% of days in first year from randomisation or up to study discontinuation or recurrence, whichever is earlier. Duration of exposure is defined using the following formula: “duration of exposure” = “last dosing date” – “first dosing date” – “days off medication” + “1 day”.

n: number of subjects; %: percentage of respective population pool treatment group; AE: adverse event; SAE: serious adverse event; SD: standard deviation; IQR: interquartile range.

Table 3: Colorectal cancer status and adjuvant therapy received

	Modified intention-to-treat		Per-protocol
	Aspirin (N=xxxx)	Placebo (N=xxxx)	
Colorectal cancer status			
Time from surgery to randomisation, day			
n	xxx	xxx	xxx
Mean (SD)	xx.x (xx.x)	xx.x (xx.x)	xx.x (xx.x)
Median (IQR)	xx.x (xx.x)	xx.x (xx.x)	xx.x (xx.x)
Min, Max	xx.x, xx.x	xx.x, xx.x	xx.x, xx.x
Type of surgery, n (%)			
Laparoscopic surgery	xxx (xx.x)	xxx (xx.x)	xxx (xx.x)
Open surgery	xxx (xx.x)	xxx (xx.x)	xxx (xx.x)
Tumour location, n (%)			
Caecum	xxx (xx.x)	xxx (xx.x)	xxx (xx.x)
Ascending colon	xxx (xx.x)	xxx (xx.x)	xxx (xx.x)
Hepatic flexure	xxx (xx.x)	xxx (xx.x)	xxx (xx.x)
Transverse colon	xxx (xx.x)	xxx (xx.x)	xxx (xx.x)
Splenic flexure	xxx (xx.x)	xxx (xx.x)	xxx (xx.x)
Descending colon	xxx (xx.x)	xxx (xx.x)	xxx (xx.x)
Sigmoid colon/ rectosigmoid colon	xxx (xx.x)	xxx (xx.x)	xxx (xx.x)
Rectum	xxx (xx.x)	xxx (xx.x)	xxx (xx.x)
T-staging, n (%)			
T1	xxx (xx.x)	xxx (xx.x)	xxx (xx.x)

T2	XXX (XX.X)	XXX (XX.X)	XXX (XX.X)	XXX (XX.X)
T3	XXX (XX.X)	XXX (XX.X)	XXX (XX.X)	XXX (XX.X)
T4	XXX (XX.X)	XXX (XX.X)	XXX (XX.X)	XXX (XX.X)
Unknown	XXX (XX.X)	XXX (XX.X)	XXX (XX.X)	XXX (XX.X)
Tumour type, n (%)				
Dukes C colon cancer	XXX (XX.X)	XXX (XX.X)	XXX (XX.X)	XXX (XX.X)
High risk Dukes B colon cancer	XXX (XX.X)	XXX (XX.X)	XXX (XX.X)	XXX (XX.X)
Rectal cancer (Dukes B or Dukes C)	XXX (XX.X)	XXX (XX.X)	XXX (XX.X)	XXX (XX.X)
Proximal margin involved	XXX (XX.X)	XXX (XX.X)	XXX (XX.X)	XXX (XX.X)
Distal margin involved	XXX (XX.X)	XXX (XX.X)	XXX (XX.X)	XXX (XX.X)
Circumferential margin involved	XXX (XX.X)	XXX (XX.X)	XXX (XX.X)	XXX (XX.X)
Histology, n (%)				
Mucinous	XXX (XX.X)	XXX (XX.X)	XXX (XX.X)	XXX (XX.X)
Adenocarcinoma	XXX (XX.X)	XXX (XX.X)	XXX (XX.X)	XXX (XX.X)
Signet ring type	XXX (XX.X)	XXX (XX.X)	XXX (XX.X)	XXX (XX.X)
Others	XXX (XX.X)	XXX (XX.X)	XXX (XX.X)	XXX (XX.X)
Unknown	XXX (XX.X)	XXX (XX.X)	XXX (XX.X)	XXX (XX.X)
Any synchronous tumours, n (%)				

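### Exposure-duration subgroups are partly defined by the DFS event, so their hazard ratios and interaction test cannot be read as a duration effect

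*SAP*

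**What the plan says.** SAP section 2 lists two subgroup variables measured after randomisation, compliance and "Duration of exposure to study drug (<1 year, 1-2 years, >2 years", under the heading of translational variables. Exposure is the number of days from first to last dose, less days off drug. SAP 4.6 treats it like country or age: "tests for interactions between treatment group and the subgroup variable of interest will be conducted first", and the results go into the forest plots for DFS and OS. No landmark, time-dependent exposure or caveat is given. SAP 4.6 does label all subgroup analyses exploratory.

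Both documents tie the end of dosing to the outcome. SAP 3.2: "The study drug will be stopped immediately if there is a disease recurrence confirmed by CT, histology or cytology". Protocol 9.3 has the same rule: "Study drug will be stopped immediately if there is disease recurrence confirmed by CT, histology or cytology". SAP section 3 counts DFS from randomisation to first recurrence or death, and mock-up Table 1 lists recurrence and death among the reasons for stopping treatment.

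Compliance is worded three ways in the SAP:

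- Section 2: "at least 70% of days in first year from randomisation or up to treatment discontinuation or recurrence, whichever is earlier".
- Section 4.2, defining the per-protocol exclusion: "those who were compliant <70% of the days in the first year from randomisation", followed by "Compliance has been defined in section 2".
- Appendix 1, note to Table 2: "up to study discontinuation or recurrence, whichever is earlier", so study discontinuation replaces treatment discontinuation.

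**The concern.** A subgroup is interpretable when membership does not depend on the outcome. Here it does. A recurrence on drug in year 1 that triggers the stop rule places the patient in the under-1-year group, and a death in year 1 does the same. That group consists of patients put there by a DFS event plus patients who stopped for other reasons. If more aspirin patients stop for other reasons, event-free stoppers dilute the aspirin side and aspirin looks better even with no effect. If stopping is equal and aspirin works, the short groups move towards 1. Either pattern can be read as benefit depending on treatment duration, which is the question readers will take to this forest plot.

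The dependence is partial. The stop rule names CT, histology or cytology, so a recurrence found only by digital rectal examination or colonoscopy need not end dosing.

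**Working it through.** **1. Anchor.** The plan gives no figure for the exposure subgroups. Its sample size (SAP 3.5) reproduces: events = 4(1.960+0.842)²/(ln 0.72)² = 4×7.85/0.1079 = 291, against 300 stated; 300/(0.21×0.90) = 1587.3. I assumed 5-year placebo DFS of 76%. With HR 0.72 aspirin is 0.76^0.72 = 0.821, and the average, 0.790, matches the pooled 79%.

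**2. Hand calculation, no drug effect.** Assume 793.5 patients per arm, 5-year follow-up, and year-1 stopping for other reasons of 15% on aspirin and 10% on placebo, unrelated to prognosis. Event hazard λ = −ln(0.76)/5 = 0.0549. Stopping hazards δ are −ln(0.85) = 0.1625 and −ln(0.90) = 0.1054.

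| Under-1-year group | Aspirin | Placebo |
|---|---|---|
| Share of arm, 1−exp(−(λ+δ)) | 0.195 (155 patients) | 0.148 (117 patients) |
| Placed there by an event, λ/(λ+δ) | 0.2525 | 0.3425 |
| Later event among the rest, 1−exp(−4.5λ) | 0.2188 | 0.2188 |
| Total with an event | 0.2525+0.7475×0.2188 = 0.416 | 0.3425+0.6575×0.2188 = 0.486 |

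(4.5 years is the approximate follow-up left after a mid-year stop.) Equal hazards in the two arms thus give event proportions of 42% and 49%.

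**3. Simulation.** 1000 replicates of 1587 patients, exponential DFS, stopping after year 1 at one third of the year-1 rate, exposure = min(DFS event, stop, 3 years), Cox HR within each group. True HR 1.00:

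| Year-1 stopping, aspirin v placebo | <1 y | 1-2 y | >2 y | Rejection, separate HRs compared | Rejection, one Cox model |
|---|---|---|---|---|---|
| 10% v 10% | 1.00 | 1.00 | 1.00 | 5% | 6-7% |
| 11% v 10% | 0.94 | 0.93 | 1.00 | | |
| 12% v 10% | 0.91 | 0.91 | 1.00 | 8% | 11% |
| 15% v 10% | 0.79 | 0.79 | 1.00 | 16% | 24-25% |
| 20% v 10% | 0.68 | 0.65 | 1.00 | 39% | 52-54% |
| 7% v 5% | 0.83 | 0.84 | 0.99 | | |

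A repeat on one very large simulated sample agreed with these HRs to within 0.02. Variants at 15% v 10%:

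- Equal stopping after year 1: 0.79 / 0.98 / 0.99.
- Follow-up varying from the 1-year minimum in SAP 4.9 up to 5 years: 0.78 / 0.86 / 1.01.

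True HR 0.72:

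- 15% v 10%: 0.58 / 0.61 / 0.72.
- 10% v 10%: about 0.75 / 0.80 / 0.73.
- 5% v 5%: about 0.79 / 0.87 / 0.72.
- Nobody stops for other reasons: about 0.98 / 0.99 / 0.70.

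So equal stopping does not protect the analysis when the drug works.

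**4. Landmark alternative, 15% v 10%, no effect.**

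- 1 year: event-free probability exp(−0.0549) = 0.947. Stopped = 793.5×0.947×(0.15+0.10) = 188 patients, with 188×(1−exp(−4×0.0549)) = 37 events.
- 2 years: stopped by then 1−0.85^(4/3) = 0.195 and 1−0.90^(4/3) = 0.131. 793.5×0.896×0.326 = 232 patients, with 232×(1−exp(−3×0.0549)) = 35 events.

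The landmark HRs were 0.99-1.02 in every null scenario with 10% placebo stopping. With a true HR of 0.72, the 1-year landmark gave 0.72 in both groups.

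**5. Compliance.** Take a patient who takes every dose for two months and quits. Under section 2 the count ends at treatment discontinuation, so the patient is compliant and stays in the per-protocol set. Section 4.2 read alone gives about 2/12 = 17% of first-year days, and the patient is removed. If such quitters are retained and have no benefit, a true 0.72 becomes about 0.90×0.72+0.10×1 = 0.75 with 10% quitters and 0.80×0.72+0.20×1 = 0.78 with 20% (simulated 0.751 and 0.771). Under the null it stays at 1.00-1.01.

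**The case against.** The analysis is exploratory, is kept apart from the baseline subgroups, and nothing else in the SAP depends on it. The over-2-year group, about 72-78% of patients in the 10%-placebo scenarios, stays near the true value. At a small imbalance (12% v 10%) the bias to 0.91 is modest beside a standard error near 0.18, and the larger imbalances are assumptions. All of this stands and limits the weight of the point. It does not remove the bias, because an exploratory label covers chance findings and this error would recur in any trial with unequal stopping. Unequal stopping is plausible: Protocol 9.2 lists gastrointestinal events for which drug is stopped, and Protocol 7.8 names gastrointestinal effects as anticipated with aspirin.

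The null model gives about 0.24×1587 = 381 events, more than the planned 300. With 79% DFS in both arms, the short groups at 15% v 10% have about 106 and 68 events rather than 122 and 78. The HRs barely change, but the standard errors rise from 0.18 and 0.23 to about 2/√106 = 0.19 and 2/√68 = 0.24. The rejection rates depend on the test model, so both sets are shown. OS was not simulated.

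On compliance, the cross-reference in SAP 4.2 largely settles the reading in favour of section 2, and the Table 2 note is probably a slip. Protocol sections 3 and 7.7 use the whole on-treatment period rather than the first year, which also needs reconciling.

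**Conclusion.** The concern holds. Exposure groups built from total time on drug are partly determined by the DFS event, and the plan has no safeguard. The size depends on stopping rates the documents do not give. With no effect and 10% placebo stopping in year 1, the short-group HRs run from 1.00 (equal stopping) to about 0.65-0.68 (20% on aspirin), and false interaction findings rise from about 5% to between 39% and 54%. With a true effect and equal stopping, the short groups are pulled towards 1. These figures assume constant hazards and stopping unrelated to prognosis. OS inherits the mechanism because recurrence precedes many deaths, but its size was not computed.

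The primary mITT DFS result is unaffected. The analysis should be changed before the final results are produced. The compliance wording is a minor editorial point: retaining early quitters dilutes the per-protocol estimate towards mITT without bias under the null.

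**What to change.** Replace the exposure-duration subgroups in SAP section 2 and 4.6 with landmark analyses at 1 and 2 years. Include patients who are alive, recurrence-free and still in follow-up at the landmark. Group them by exposure up to it (stopped before v still on drug), count DFS and OS from the landmark, and label the comparison non-randomised. Keep two groups per landmark: at 15% v 10%, patients stopping between 1 and 2 years would number only about 54, with 8 events.

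Separately, use one compliance definition in SAP section 2, SAP 4.2 and the Table 2 note, and state how it relates to Protocol sections 3 and 7.7. Describe the per-protocol analysis as measuring adherence while on drug. If a set excluding early quitters is wanted, add it as a further sensitivity analysis and state that the exclusion is post-randomisation and may differ by arm.

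The cost is SAP wording and modest programming on data already collected. The loss is precision: with 35-37 events in the stopped groups, the standard error of the log HR is about 0.34-0.36. If that is judged too imprecise to report, describing exposure by arm in Table 2 without subgroup HRs also avoids the problem.

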3 STUDY ENDPOINTS

Primary endpoint

DFS is defined as the time from randomisation to the time of documentation of first disease recurrence or death from any cause. If there is no disease recurrence or death by the time when a subject is last followed up, it will be censored at that time.

The disease recurrence is defined as any one of the followings:

- Unequivocal radiological evidence of colorectal cancer recurrence
- Recurrence detected by digital rectal examination (DRE)
- Positive histology or cytology (i.e. peritoneal or pleural cytology)
- Colonoscopic evidence of local cancer recurrence at the previous operation site
- Detection of a new colon or rectal primary tumour

Secondary endpoints

OS is defined as the time from randomisation to the time of death from any cause. If there is no death by the time when a subject is last known to be alive, it will be censored at that time.

Exploratory endpoints

Exploratory endpoints involve DFS and OS in subgroups, as well as recurrence free survival. Recurrence free survival is defined as time from randomisation to first disease recurrence.

1 TRIAL DESIGN

1.1 Study Population

The study population consists of Dukes C colon cancer, high risk Dukes B colon cancer, Dukes B rectal cancer or Dukes C rectal cancer subjects who have completed the resection of primary tumour. The population will be treated with standard therapy (chemotherapy ± radiotherapy). During the last cycle of standard therapy, patients would be invited to

participate in this study. Once informed consent is taken and within 120 days of completion of the standard therapy, they would be checked for trial eligibility.

Inclusion Criteria

- Male or female outpatient of ≥ 18 years of age or \geq country's legal age for adult consent
- Dukes C colon cancer, high risk Dukes B colon cancer, Dukes B rectal cancer or Dukes C rectal cancer
- Undergone complete resection of primary tumour
- Completed standard therapy (at least 3 months of chemotherapy \pm radiotherapy)
- Within 120 days of completion of standard therapy (surgery, chemotherapy \pm radiotherapy)
- Eastern Cooperative Oncology Group (ECOG) performance status 0 to 2
- Satisfactory haematological or biochemical functions (tests should be carried out within 8 weeks prior to randomisation): Results of clinical investigations carried out within 8 weeks prior to randomisation can be used in place of the required screening investigations. Patients with mild laboratory abnormalities can be included at the discretion by the site principal investigator, and after approval by ASCOLT Trial Management Group
 - ANC $\geq 1.0 \times 10^9/L$
 - Platelets $\geq 100 \times 10^9/L$
 - Creatinine clearance ≥ 30 mL/min
 - Total bilirubin ≤ 2.0 x the upper limit normal
 - AST & ALT ≤ 5 x the upper limit normal

Completed the following investigations

- Colonoscopy (or CT colonogram (within 16 months prior to randomization))
- Imaging of abdomen (CT or CT colonogram or MRI or PET or Ultrasound) within 16 months prior to randomization
- Written informed consent

Exclusion Criteria

- Pre-existing familial adenomatous polyposis, inflammatory bowel disease or ulcerative colitis
- Active gastritis or active peptic ulcer
- History of continuous daily use of proton pump inhibitor (PPI) more than 1 year prior to consent
- Gastrointestinal bleeding within the past one year
- Haemorrhagic diathesis (i.e. haemophilia)
- Uncontrolled hypertension (untreated systolic blood pressure > 160 mmHg, or diastolic blood pressure > 95 mmHg)
- History of recent cancers (except for colorectal cancers, non melanoma skin cancers, basal cell carcinomas, squamous cell carcinomas) in the past 5 years
- History of stroke, coronary arterial disease, angina, or vascular disease
- Patients who are on current long term treatment (≥ 4 consecutive weeks) with Aspirin, NSAID or Cox-2 inhibitors
- History of erosive GERD or active erosive GERD on gastroscopy.
- Patient on active current treatment with antiplatelet agents (i.e. off-study Aspirin, clopidogrel, ticlopidine)
- Patient receiving current treatment with anticoagulants (i.e. warfarin, low molecular weight heparins)
- Pregnant, lactating, or not using adequate contraception
- Patient having known allergy to NSAID or Aspirin
- Unexplained rise of CEA (i.e. smoker with elevated CEA will not be excluded)
- Patient on other investigational drug
- Patient with HNPCC (Lynch Syndrome)

